2.8.3 Treatment Plan Selection

The simulation CT images will be electronically transferred to the Eclipse treatment planning workstation (Varian, Palo Alto, CA; Eclipse is used without modification to the present 510(k) clearance) and the target site(s) will be delineated by one of the radiation oncologist investigators. A single-field 250 MeV transmission plan will be chosen from a pre-defined library of plans having different field sizes (see section 2.7). Based on a review of bone metastases cases treated at the investigational site over a 12-month period, these field sizes will be adequate to treat sufficient patients successfully. Plans will be matched for each of the FLASH treatment sites (up to 3 FLASH treatment sites for each subject). Using image guidance, clinical lesions up to 6.5 cm in diameter will be treated. A Planning Tumor Volume (PTV) margin of ≥ 5 mm will be added to the Gross Tumor Volume/Clinical Target Volume (GTV/CTV). There will be no GTV to CTV margin. This is consistent with standard clinical practice in the palliative

treatment of bone metastases. Patients who cannot be treated using the pre-defined treatment field sizes will be removed from the study and replaced.

The pre-defined plans are designed to deliver a prescription of 8 Gy in a single fraction at ≥ 40 Gy/s to the PTV. Since the treatment will be delivered with transmission FLASH, there will be no Bragg Peak within the body; the relative biological effectiveness (RBE) of 1.0 will, therefore, apply since no correction is required for Bragg Peak. The volume of PTV receiving 90% of the prescribed dose shall be greater than or equal to 90%, and the dose to 10% of the PTV will not exceed 110%. The prescribed dose of 8 Gy in a single fraction is a standard fractionation for painful bone metastases whose efficacy has been validated in prior multi-institutional prospective randomized clinical trials [10, 11].

2.8.4 QA

There are two forms of QA routinely performed for treatment with standard dose rate proton radiation. The first is daily machine QA and the second is patient specific QA. Patient specific QA for subjects treated on this FLASH study protocol may be performed, for example, using film and ion chamber dosimetry. An additional QA procedure will be performed on the day of treatment prior to the subject's treatment confirming the FLASH dose and dose rate constancy of the proton delivery system.

2.8.5 FLASH Radiotherapy Delivery (Day 1)

The treatment plan will be transferred from the ARIA Oncology Information System (Varian, Palo Alto, CA; ARIA is used without modification to the present 510(k) clearance) to the FLASH enabled ProBeam Proton Therapy System console for FLASH radiotherapy delivery. Subjects will be positioned on the treatment couch as determined at the time of their simulation visit. Image guidance will be used to verify that the target is in the correct position for treatment. The treatment will be carried out for up to 3 treatment sites for each subject, depending on the total number of painful bone metastases in limb bones (excluding feet, hands, wrists) to be treated.

On the day of treatment, but before start of treatment, the following baseline data will be recorded: patient reported pain score overall and specifically at each treated site (see section 2.8.6 for questionnaires to be used); subject evaluation (use of pain medication (including steroid medications), performance status, photographs of skin and any physical findings on examination involving the skin or other normal tissue in the treatment site(s)).

2.8.6 Pain Assessment Questionnaires

There are several questionnaires used in this study as described below:

Brief Pain Inventory (BPI) short form questionnaire:

Patient reported pain score (overall) at baseline and post-treatment (Day 15, Month 1, Month 2, Month 3, long-term) will be assessed using the BPI short form questionnaire (see section 2.2.2 Schedule of Activities table).

The BPI short form questionnaire was employed in a prior cooperative-group (Radiation Therapy Oncology Group) prospective, phase III, randomized study evaluating the efficacy of 8 Gy radiation for the treatment of painful bone metastases [10]. Using the BPI short form questionnaire will allow comparison of the current study results to these historical data. This form assesses overall pain response without focus on an individual metastasis.

Treated Sites Pain questionnaire:

Additionally, patient reported pain for each treated site at baseline and post-treatment (Day 15, Month 1, Month 2, Month 3, long-term) will be assessed using a four item subset of the questions from the BPI questionnaire (see section 2.2.2 Schedule of Activities table). This form assesses pain response in each treated site.

Pain Flare questionnaire:

An additional three item questionnaire is required only at baseline and for the first 10 days after treatment to assess radiation treatment related flare in bone pain for each treated site (see section 2.2.2 Schedule of Activities table). The questionnaire uses the methodology employed by Chow et al. [12] to specifically identify flare in bone pain. The patient reported questionnaire will be used to collect the following information: for each treated site, worst pain over the last 24 hours and comparison of this worst pain to the worst pain in the treated site on the day of treatment; pain medications usage, including steroid medications.

2.8.7 Adverse Event Checks

Adverse events will be monitored from start of treatment to completion of the final study follow-up visit. Adverse event checks will take place on the day of treatment (Day 1 after treatment delivery) and at the follow-up visit time points Day 15, Month 1, Month 2, Month 3, and long-term follow-up (see section 2.2.2 Schedule of Activities table). The adverse event check on Day 2 will be carried out by remote review. All other adverse event checks during follow-up may be carried out using a combination of remote visits and/or records review as an alternative to in-person visits to accommodate the subject's inability or reluctance to travel. Adverse event checks will be recorded on the corresponding case report form. All adverse events will be collected regardless of severity or attribution. Adverse events will be classified per CTCAE version 5.0.

2.8.8 Follow-Up

During the first 10 days after completion of FLASH radiotherapy, subjects will complete a questionnaire daily to assess radiation treatment related flare in bone pain for each treated site (see section 2.8.6 for questionnaires to be used; see section 2.2.2 Schedule of Activities table).

Subjects are expected to have in-person follow-up visits at Day 15 (+/- 2 business days), Month 1 (+/- 5 business days), Month 2 (+/- 10 business days), and Month 3 (+/- 10 business days); long-term follow-up 2 months (+/- 10 business days) beyond Month 3, until subject death or lost to follow-up.

For the Day 15, Month 1, Month 2, Month 3 follow-up visits, the following data will be recorded:

- Patient reported pain score overall and specifically at each treated site (see section 2.8.6 for questionnaires to be used; see section 2.2.2 Schedule of Activities table)
- Subject evaluation: use of pain medications (including steroid medications), performance status, physical evaluation including photographs of skin and any physical findings on examination involving the skin or other normal tissue in the treatment site(s)
- Adverse event evaluation (including skin and other normal tissue toxicities)
- It is desirable to have follow-up visits in-person. However, it is acceptable to carry out remote follow-up visits as an alternative in the event of the subject's inability or reluctance to travel given the current COVID-19 pandemic. In these circumstances, photographs of the treatment site may be taken at home by caregivers, and physical evaluation will be carried out to the extent that is feasible via telehealth.

Long-term follow-up visits beyond Month 3 may be carried out using a combination of remote visits and/or records review as an alternative to in-person visits to accommodate the subject's inability or reluctance to travel. The following data will be recorded:

- Patient reported pain score overall and specifically at each treated site (see section 2.8.6 for questionnaires to be used; see section 2.2.2 Schedule of Activities table). Questionnaires will be completed as subject's clinical status permits.
- Subject evaluation (use of pain medication (including steroid medications), performance status, physical evaluation)
- Adverse event evaluation (including skin and other normal tissue toxicities)

Follow-up visits that are in-person (Day 15, Month 1, Month 2, Month 3) and any in-person visits during long-term follow-up will take place at a location(s) listed in section 9, as determined by mutual convenience of the subject and investigator.

Choice of follow-up visit time points was informed by the study designs of Chow et al. [12] and Hartsell [10].

Patients may continue to take steroids during their participation in the clinical trial if prescribed by their physician. Steroid medication is optional and at the discretion of the prescribing physician.

Subject study participation will end following subject death or lost to follow-up.

2.9 Adverse Events

Adverse event evaluation and management will be conducted by the investigator or his/her designee (must be study physician, nurse, or PA/ARNP). Radiation dermatitis within the irradiated field is the adverse event that would be most likely to occur. This adverse event would be managed as an outpatient treatment at the locations listed in section 9 by the investigator or his/her designee using an appropriate combination of topical emollients, topical steroids, topical antibiotics, and dressings as determined to be necessary by the investigator or designee. Other adverse events that might occur such as pathologic fracture of the treated bone would be referred to the appropriate specialist for management (note that pathologic fracture of a bony metastasis is a known complication of the disease process).

The CTCAE version 5.0 defines an adverse event (AE) as follows: "Any unfavorable and unintended sign (including an abnormal laboratory finding), symptom, or disease temporally associated with the use of a medical treatment or procedure that may or may not be considered related to the medical treatment or procedure. An AE is a term that is a unique representation of a specific event used for medical documentation and scientific analyses."

AEs will be given an attribution by the investigator as follows:

- Definitely related to the FLASH radiotherapy delivery
 - AE has timely relationships to the investigational device administration and there is no known alternative etiology responsible for the AE.
- Probably related to the FLASH radiotherapy delivery
 - AE has a timely relationship to the investigational device administration. No potential alternative etiology is apparent.
- Possibly related to the FLASH radiotherapy delivery
 - AE has a timely relationship to the investigational device administration; however, a potential alternative etiology may be responsible for the AE.
- Unlikely (Probably not) related to the FLASH radiotherapy delivery
 - There is no definitive evidence that the AE has a relationship to the investigational device. It was either present before the study, a symptom(s) of primary disease, or due to use of concomitant medications.
- Definitely not related to the FLASH radiotherapy delivery
 - There is clearly no evidence that the AE has a relationship to the investigational device.

The investigator will document whether the AE is attributable to the FLASH radiotherapy delivery.

Grades will be assigned to clinical AEs by the investigator or his/her designee per the CTCAE version 5.0, which consists of a scale from 1 to 5 to describe the severity of the AE. A copy of the CTCAE version 5.0 will be provided. For reference, an overview of the grades is given below, but the CTCAE v5 needs to be consulted for specific grading criteria:

- Grade 1 – Mild, asymptomatic or mild symptoms; clinical or diagnostic observations only; intervention not indicated.
- Grade 2 – Moderate; minimal, local or noninvasive intervention indicated; limited age-appropriate instrumental activities of daily living (ADL). Instrumental ADL refer to preparing meals, shopping for groceries or clothes, using the telephone, managing money, etc.
- Grade 3 – Severe or medically significant but not immediately life-threatening; hospitalization or prolongation of hospitalization indicated; disabling; limiting self-care ADL. Self-care ADL refer to bathing, dressing and undressing, feeding self, using the toilet, taking medications, and not bedridden.

- Grade 4 – Life-threatening consequences; urgent intervention indicated.
- Grade 5 – Death related to AE.

There are anticipated adverse events associated with the delivery of 8 Gy radiation in a single fraction at standard dose rate for the treatment of bone metastases. The frequency and severity of these toxicities were evaluated at standard dose rates in a prior benchmark multi-institutional prospective randomized clinical trial [10]. In this trial, a cohort of 455 patients (433 and 354 patients analyzed for acute and late toxicities, respectively) were treated with 8 Gy for palliation of painful bone metastases. Grade 2-3 acute toxicity (within 90 days after starting radiation therapy) occurred in 10% of the patients, and “late toxicity was rare (4%)”. The most common toxicity was gastrointestinal, which accounted for approximately half of all acute adverse events. Gastrointestinal toxicity should not be relevant to the present feasibility study as treatment is limited to the extremities. No patients in the cited study receiving 8 Gy had Grade 4 acute or late toxicities.

It is expected that the majority of toxicities in the present clinical study will be related to the skin. In the prior cited study, there were no acute or late grade 3 or grade 4 skin toxicities in patients treated with 8 Gy at standard dose rates. Of the 433 patients, acute grade 1/ grade 2 / grade 3 / grade 4 skin toxicities occurred in 15 / 1 / 0 / 0 patients, respectively. Acute grade 1 / grade 2 / grade 3 / grade 4 hematologic toxicities occurred in 10 / 7 / 2 / 0 patients, respectively. “Other” (not specified) acute grade 1 / grade 2 / grade 3 / grade 4 toxicities occurred in 11 / 6 / 6 / 0 patients, respectively. These toxicities were scored using the (RTOG) Acute and Late Morbidity Criteria. This grading system has since been supplanted by the CTCAE system. For the great majority of toxicities (skin) expected in the present clinical study, the RTOG skin and CTCAE radiation dermatitis scoring systems are very similar. In addition, the hematologic scoring criteria for both RTOG and CTCAE are very similar or can be readily numerically converted for comparison purposes.

Serious Adverse Events

Per ISO 14155:2011, the following definitions apply:

- A Serious Adverse Event (SAE) is any untoward medical occurrence, unintended disease or injury, or untoward clinical signs (including abnormal laboratory findings) in subjects, users or other persons, whether or not related to the investigational medical device* that:
 - Led to a death,
 - Led to serious deterioration in the health of the subject, that either resulted in
 - a life-threatening illness or injury, or
 - a permanent impairment of a body structure or a body function, or
 - in-patient or prolonged hospitalization**, or
 - medical or surgical intervention to prevent life-threatening illness or injury or permanent impairment to a body structure or a body function
 - Led to fetal distress, fetal death or a congenital abnormality or birth defect.

***NOTES:**

- NOTE 1 This definition includes events related to the investigational medical device or the comparator.
- NOTE 2 This definition includes events related to the procedures involved.
- NOTE 3 For users or other persons, this definition is restricted to events related to investigational medical devices.

**NOTE Planned hospitalization for a pre-existing condition, or a procedure required by the CIP, without serious deterioration in health, is not considered a serious adverse event.

Hospitalization means admitted to hospital for at least 24 hours. An emergency room, urgent care, or infusion center visit is not a hospitalization.

Per the US Code of Federal Regulations, Title 21, Part 812, the following definition applies:

- Unanticipated adverse device effect (UADE) means any serious adverse effect on health or safety or any life-threatening problem or death caused by, or associated with, a device, if that effect, problem, or death was not previously identified in nature, severity, or degree of incidence in the clinical investigational plan or application (including a supplementary plan or application), or any other unanticipated serious problem associated with a device that relates to the rights, safety, or welfare of subjects.

Adverse Event Reporting

The Investigator will notify the Sponsor of all serious adverse events (SAEs), including UADEs, by phone or email as soon as possible but no later than within 24 hours of learning of an event.

Sponsor Contact Information for Adverse Event Reporting:

[name]

[contact]

[name]

[contact]

████████ (voicemail) or ██████████ (mobile)

It is the responsibility of each Investigator to report all reportable adverse events and other reportable events to the Institutional Review Board (IRB) according to the requirements of the IRB.

Per the US Code of Federal Regulations, UADEs will be reported and evaluated as required in 21 CFR Part 812.

2.10 Device-Related Issues

Any problems with the FLASH radiotherapy delivery (including any device failures or malfunctions) will be documented and reported to the Sponsor.

Per ISO 14155:2011, the following definition applies:

- Device Deficiency: inadequacy of a medical device with respect to its identity, quality, durability, reliability, safety or performance

NOTE Device deficiencies include malfunctions, use errors, and inadequate labeling.

2.11 Protocol Deviations and Other Study Problems

The investigator is not allowed to deviate from the CIP, except in emergency situations in order to protect the rights, safety, and well-being of the subjects. Protocol deviations and other problems with study execution will be documented and reported to the Sponsor and the IRB promptly.

2.12 Subject End of Study

The Subject End of Study case report form will be completed in the following situations:

- The subject completed the study per protocol
- The investigator terminated the subject's participation
- The subject withdrew from the study
- The subject was lost to follow-up (after a minimum of two phone calls on separate days and within a week of a certified letter being delivered)
- The subject died on study
- The Sponsor terminated the study

If the subject leaves the study for any reason before the next scheduled follow-up visit is completed, the investigator will document the reason(s). In addition, the investigator will attempt to collect the following: patient reported pain score overall and specifically for treated site(s), use of pain medications (including steroid medications), and adverse events (including skin and other normal tissue toxicities).

An investigator may withdraw the subject's participation in the study for one or more of the following reasons:

- Significant non-compliance with the study procedures

- If an adverse event, laboratory abnormality, or other medical condition or situation occurs such that continued participation in the study would not be in the best interest of the subject
- If the subject meets an exclusion criterion (either newly developed or not previously recognized) that precludes further study participation

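### Section 2.12 lets a subject be closed as lost to follow-up without a records check, and nothing collects toxicities after closure, although the plan already allows records review for adverse events

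*Combined protocol and SAP*

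**What the plan says.** - **Closure rule (2.12).** The end-of-study form is completed for a subject lost to follow-up "after a minimum of two phone calls on separate days and within a week of a certified letter being delivered". No check of records or vital status is attached.
- **Effect of closure (2.8.8).** "Subject study participation will end following subject death or lost to follow-up".
- **Exit step (2.12).** When a subject leaves for whatever reason before the next visit is completed, the investigator records why and tries to obtain pain scores, pain medication and adverse events. No source is named for a subject who cannot be reached.
- **Adverse event collection (2.8.7).** "Adverse events will be monitored from start of treatment to completion of the final study follow-up visit". Also: "All adverse events will be collected regardless of severity or attribution".
- **Permitted methods.** Section 2.8.7, after setting Day 2 as a remote review, says: "All other adverse event checks during follow-up may be carried out using a combination of remote visits and/or records review". Section 2.8.8 says: "Long-term follow-up visits beyond Month 3 may be carried out using a combination of remote visits and/or records review". For Day 15 to Month 3, section 2.8.8 and footnote 2 of the schedule (2.2.2) offer only a remote visit in place of an in-person one: "it is acceptable to carry out remote follow-up visits as an alternative in the event of the subject's inability or reluctance to travel".
- **Use of the data (2.5, 2.13).** Toxicities at least possibly related to FLASH are a primary outcome. DLTs are counted over the whole study, and three subjects with a DLT trigger a stopping rule.
- **Numbers (2.8.1, 2.13).** Up to 10 subjects. Those who leave after treatment count towards the limit and are not replaced.

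**The concern.** Follow-up is meant to be open-ended, and the revision history gives longer toxicity assessment as the reason. The risks listed in 3.1 include late effects such as fibrosis, necrosis, fracture and secondary malignancy. Open-ended follow-up is only as complete as the rule that closes it.

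That rule looks solely at whether the subject answers. Whether adverse event data can still be obtained is a separate question, and elsewhere the plan accepts the chart as a source that needs no answer from the subject. A silent subject can thus be closed while toxicities, or a death, could still be read from the record. At stake are the completeness of a primary outcome and of the DLT count.

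**Working it through.** The documents state no power, precision target, loss rate or sample-size derivation, so there is no figure to reproduce. The check is mainly of the text, with illustrative arithmetic for size.

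**1. Sections side by side**

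| Period | Is adverse event information obtainable without contact? | Does the plan require it? |
|---|---|---|
| Up to closure | Yes by 2.8.7 (all follow-up checks except Day 2). Beyond Month 3, also by 2.2.2 footnote 3 and 2.8.8 | An attempt at exit (2.12), source not named |
| After closure | From the chart, if one exists | No: participation has ended (2.8.8) |

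The gap therefore has two parts: no required records check before closure, and no collection after it. Section 2.12 also gives no route back for a subject who is found later.

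**2. Two wording points**

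- The one-week term can mean that closure takes place within a week of delivery, or that no reply has come within a week of delivery. These give different earliest closure dates, and the text does not settle which applies.
- From Day 15 to Month 3, 2.8.7 permits records review for adverse event checks, while 2.2.2 and 2.8.8 name only remote visits. The sections need to be reconciled.

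**3. Size per subject**

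With at most 10 treated and none replaced, one closure ends later observation of at least 1/10 = 10% of subjects.

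**4. Illustration for the three-DLT rule (rates assumed)**

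Let p be the true share of subjects with a DLT (assumed 10% to 30%) and m the share of those DLTs missed after closure (assumed 0% to 30%). With 10 subjects and q = p(1 − m):

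P(at least 3) = 1 − Σ over k = 0 to 2 of C(10,k) q^k (1 − q)^(10 − k)

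For p = 0.20, m = 0: 1 − (0.1074 + 0.2684 + 0.3020) = 0.322. For p = 0.20, m = 0.20, so q = 0.16: 1 − (0.1749 + 0.3331 + 0.2856) = 0.206.

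| p | m = 0 | m = 20% | m = 30% |
|---|---|---|---|
| 10% | 7.0% | 4.0% | 2.8% |
| 20% | 32.2% | 20.6% | 15.5% |
| 30% | 61.7% | 44.4% | 35.3% |

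If m is read as the share of subjects lost, unrelated to risk, these results are upper limits on the effect: they take every DLT in a lost subject as unseen, whereas some would be recorded before closure or at the exit step.

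**5. Illustration for the toxicity summary**

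With no DLT seen in n fully followed subjects, the one-sided 95% upper bound is 1 − 0.05^(1/n): 25.9% for n = 10, 31.2% for n = 8, 34.8% for n = 7. The plan does not call for this bound. It shows only how little room 10 subjects leave for loss.

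**The case against.** The strongest reply is that 2.12 does not work alone. It requires an attempt to collect adverse events at exit, and for an unreachable subject the chart is the natural source. It lists when a form is completed and does not oblige the investigator to declare a silent subject lost. Beyond Month 3, a visit done from records may count as carried out, in which case the subject is not lost. Some study activities also take place at routine oncology visits (2.8).

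Much of this stands. The exit step covers events up to closure if records are used, and a careful investigator could avoid closure altogether. But the text neither requires the records check nor says that an informative chart keeps the subject in follow-up. Records review is offered to accommodate subjects who cannot or would rather not travel; it is not described as a tracing method. Nothing covers events after closure.

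Three stronger readings are tempting and are not supported:

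- *The rule removes the sickest subjects and so understates toxicity.* The plan expects a guarded prognosis, but no section links illness to loss. Uncounted events can only lower the count. Whether a rate among those still followed is too high or too low depends on the risk of those lost and on the denominator, which 2.13 does not set.
- *One missed contact is enough, and closure follows within days.* At least two calls on separate days and a delivered certified letter are needed, two calls is a floor, and the timing depends on an ambiguous phrase.
- *A missed late DLT lets enrollment continue when it should stop.* Triggering the rule ends enrollment and prompts a data review (2.13). Enrollment is expected to take 12 months (1.3). A DLT that arises after enrollment has closed cannot affect it, though it still bears on the review and on the reported toxicity.

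**Conclusion.** The point holds in a limited form. Section 2.12 permits closure on failed contact without a required records check, and adverse events after closure are not collected, although the plan accepts records review as an adverse event method and counts DLTs over the whole study. Late related toxicities can therefore go uncounted while still obtainable from the chart.

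The size is at least 10% of treated subjects per closure; beyond that it is not known. The probabilities above rest on assumed DLT and loss rates and show what could happen, not what is expected. The conclusion also assumes that an unreachable subject has a chart the site can consult. In a descriptive feasibility study of up to 10 subjects this is a change to consider. It goes beyond a request for detail because it alters a stated rule, using a method the plan already has.

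**What to change.** Replace the lost-to-follow-up item in 2.12 with wording such as:

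> A subject who has not withdrawn consent is classed as lost to follow-up only when (i) at least two calls on separate days and a certified letter have brought no response by at least one week after the letter was delivered, and (ii) a documented check of medical records and vital status gives no information for that visit. Where records are informative, adverse event follow-up continues by records review at the scheduled visits. A subject found later returns to follow-up, and adverse events in the gap are collected from records.

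Also reconcile 2.8.7 with 2.2.2 and 2.8.8 on whether records review is allowed from Day 15 to Month 3, since the 2.12 rule applies in that period too. A line in 2.13 on how subjects lost early are counted in the toxicity summary would be a useful optional addition.

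Cost: a few sentences, one chart and vital-status check per unreachable subject, continued chart review for those whose records are informative, and slightly later closure. No new visits or procedures for subjects.
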